### **12.2.2 Local Skin Reactions**

The frequency of local skin reactions including itching, dryness, burning/stinging, skin atrophy, striae, telangiectasia and folliculitis will be summarized by treatment group and visit. Additionally, the percent of subjects who experience a local skin reaction (itching, dryness, burning/stinging) graded at a level of 3, at any point in the study following the first application of study drug, will be tabulated by treatment group.

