0	None	No itching																																														
1	Mild	Slight itching, not really bothersome																																														
2	Moderate	Definite itching that is somewhat bothersome																																														
3	Severe	Intense itching that may interrupt daily activities and/or sleep																																														
Dryness: as assessed by the investigator																																																
0	None	No dryness																																														
1	Mild	Slight, but definite roughness																																														
2	Moderate	Definite roughness																																														
3	Severe	Marked roughness																																														
Burning/Stinging: as reported by the subject within the last 24 hours																																																
0	None	No burning/stinging																																														
1	Mild	Slight burning/stinging sensation; not really bothersome																																														
2	Moderate	Definite warm, burning/stinging that is somewhat bothersome																																														
3	Severe	Hot burning/stinging sensation that causes definite discomfort and may interrupt daily activities and/or sleep																																														

All of the below will be assessed by the investigator as present or absent.	
Skin Atrophy:	
No	Skin atrophy not present
Yes	Skin atrophy present
Striae:	
No	Striae not present
Yes	Striae present
Telangiectasias:	
No	Telangiectasias not present
Yes	Telangiectasias present
Folliculitis:	
No	Folliculitis not present
Yes	Folliculitis present

**Adverse Events:** During the study, subjects will be assessed for the occurrence of new and ongoing AEs. Descriptions of AEs will include the dates of onset and resolution (if resolved), maximum severity, seriousness, action taken regarding the study drug, corrective treatment, outcome, and the investigator's assessment of causality. AEs present at any visit will be followed to resolution (return to normal or to the baseline state) or until clinically stable as determined by the investigator.

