## 5 Introduction

Psoriasis is a chronic, immune-mediated disease that varies widely in its clinical expression. Disease severity ranges from mild (limited number of plaques) to very severe. Characteristic features of psoriasis include hyperproliferation of epidermal cells associated with dermal/epidermal inflammation, resulting in sharply demarcated red plaques, which may be covered by silvery scales affecting the skin and scalp.

There are presently no curative treatments for psoriasis. Treatment options focus on relieving symptoms, reducing inflammation, induration, and scaling, and controlling the extent of the disease. Patient age, severity of disease, and the type and extent of body surface area (BSA) involvement are considerations in selecting therapy.

Biologic treatments are now either available or in development to treat psoriasis. However, these treatments are not typically used for mild disease, and their safety profile is not entirely well understood.

Topical therapies are used in all disease severities, but may be impractical when psoriasis involves a large BSA. The mainstay of psoriasis treatment is topical corticosteroids, which range in potency from superpotent to low potency (Class I to Class VII, respectively). Generally, the more potent corticosteroids are required for effective management of psoriasis.

Although topical corticosteroids are very effective, long-term safety remains a concern, particularly with the more potent ones. Adverse effects such as skin atrophy, telangiectasia, and potential hypothalamic-pituitary-adrenal axis suppression have been associated with higher potency topical corticosteroids and prolonged treatment. Ultravate® cream and ointment (halobetasol propionate [HP] 0.05%) is currently on the market and are classified as super-high potency (Class I) corticosteroids indicated for the relief of the inflammatory and pruritic manifestations of corticosteroid-responsive dermatoses.

Having a lower concentration product that is a Class I steroid might be advantageous for patients, as the steroid provides relief from inflammation, and may reduce the adverse reactions associated with a steroid (eg, skin atrophy).

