## 11.3 Evaluation of Safety

### 11.3.1 Localized Skin Reactions

Tolerability will be evaluated through assessments of selected local signs and symptoms (itching, dryness, and burning /stinging). In addition, the treatment areas will be examined by the evaluator at each visit for presence or absence of significant known drug-related AEs; skin atrophy, striae, telangiectasia, and folliculitis. Any local skin reaction requiring use of a concomitant therapy or is a cause for study drug interruption or discontinuation should be reported as an adverse event. The scales to be used for assessing local skin reactions are shown in

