**Table 4. Localized Skin Reaction Scales**

Score	Grade	Description
Itching: as reported by the subject within the last 24 hours		
0	None	No itching
1	Mild	Slight itching, not really bothersome
2	Moderate	Definite itching that is somewhat bothersome
3	Severe	Intense itching that may interrupt daily activities and/or sleep
Dryness: as assessed by the investigator		
0	None	No dryness
1	Mild	Slight, but definite roughness
2	Moderate	Definite roughness
3	Severe	Marked roughness
Burning:/Stinging: as reported by the subject within the last 24 hours		
0	None	No burning/stinging
1	Mild	Slight burning sensation; not really bothersome
2	Moderate	Definite warm, burning that is somewhat bothersome
3	Severe	Hot burning sensation that causes definite discomfort and may interrupt daily activities and/or sleep
All of the below will be assessed by the investigator as present or absent.		
Skin Atrophy:		
No	Skin atrophy not present	
Yes	Skin atrophy present	
Striae:		
No	Striae not present	
Yes	Striae present	
Telangiectasias:		
No	Telangiectasias not present	
Yes	Telangiectasias present	
Folliculitis:		
No	Folliculitis not present	
Yes	Folliculitis present	

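### Section 12.2.2 prespecifies no any-time or new-onset proportion for skin atrophy, striae, telangiectasia or folliculitis, and the AE rules do not clearly fill the gap

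*Combined protocol and SAP*

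**What the plan says.** Section 12.2.2, and the synopsis in the same terms, plans two summaries of local skin reactions.

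- The first is a frequency table for all seven reactions. For the four signs at issue it reads "skin atrophy, striae, telangiectasia and folliculitis will be summarized by treatment group and visit".
- The second is an any-time, per-subject figure: "the percent of subjects who experience a local skin reaction (itching, dryness, burning/stinging) graded at a level of 3, at any point in the study", counted after the first application and tabulated by arm.

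The four signs cannot enter the second summary, because Table 4 does not grade them: "All of the below will be assessed by the investigator as present or absent". Table 1 has local skin reactions evaluated at Baseline, Weeks 2, 4, 6, 8 (or early termination) and 12. Section 12 states that missing safety data are not imputed.

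On AE status, Section 11.3.1 has each visit's examination look for "presence or absence of significant known drug-related AEs; skin atrophy, striae, telangiectasia, and folliculitis". The next sentence says that any local reaction "requiring use of a concomitant therapy or is a cause for study drug interruption or discontinuation should be reported as an adverse event". Section 11.5.2 has a similar sentence that lists therapy or discontinuation but not interruption. Section 11.5.1 defines an AE broadly, to include an unfavorable sign that appears or worsens, with no action threshold. For events that are AEs, the synopsis says: "AEs present at any visit will be followed to resolution (return to normal or to the baseline state) or until clinically stable".

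**The concern.** For a topical corticosteroid, a reader of the safety report will ask what share of subjects newly developed atrophy, striae or telangiectasia, and whether it resolved. The Introduction names atrophy and telangiectasia as corticosteroid risks and offers less atrophy as a possible benefit of a lower concentration. The synopsis gives skin atrophy as an example of a reaction that could lead to dosing being halted. Yet the three graded reactions get a cumulative per-subject figure and these four signs do not.

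The by-visit table has two weaknesses for this question. It cannot link a subject's findings across visits, so different subjects affected at different visits are never added up. It also does not separate a sign already present at Day 0 from one that arose on treatment. If AE reporting captured every new sign, the TEAE table would answer the question, but the AE wording leaves that open.

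**Working it through.** **1. Inputs.** The plan states no figure on this point and no expected rate or duration for these signs. The planned active arm is 140 subjects (Section 12.8.2). There are five post-baseline assessments: Weeks 2, 4, 6, 8 and 12 (Table 1). All case counts below are assumptions for illustration.

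**2. What by-visit counts can show.** If c1 to c5 are the numbers with a sign at the five visits, the number ever affected after Baseline lies between the largest count and the sum of the counts. The table alone cannot narrow that range.

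**3. Example with four on-treatment visits.** Assume 2 new cases at each of Weeks 2, 4, 6 and 8, all in different subjects.

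- If each sign has cleared, or the subject is absent, by the next visit, each visit shows 2/140 = 1.4%. The number ever affected is 4 × 2 = 8, and 8/140 = 5.7%. The ratio is 8/2 = 4.
- If all signs persist and all subjects stay, the counts are 2, 4, 6 and 8. Week 8 shows 8/140 = 5.7%, with no understatement.

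**4. Example with all five post-baseline visits.** Let k subjects be affected, each seen with the sign at v of 5 visits. Mean visit prevalence is k × v / (5 × 140), and the any-time proportion is k/140. The understatement factor is 5/v.

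| k | Any-time | v = 1 | v = 3 | v = 5 |
|---|---|---|---|---|
| 5 | 3.57% | 0.71% | 2.14% | 3.57% |
| 10 | 7.14% | 1.43% | 4.29% | 7.14% |

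The factor runs from 1 (v = 5) to 5 (v = 1).

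**5. Baseline findings.** Suppose 10 of 140 show a sign at Week 8 and 5 of them had it at Day 0. The Week 8 row shows 10/140 = 7.14%. New onset is 5 of the 135 without the sign at Day 0, or 5/135 = 3.70%. Subtracting a Baseline row gives only the net change: a Baseline sign that clears cancels a new one. So the table can also overstate new onset.

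**6. The AE texts side by side.**

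| Place | When a local sign is an AE |
|---|---|
| Section 11.3.1; synopsis, Safety Measurements | Therapy, interruption or discontinuation; the same text also calls the four signs known drug-related AEs |
| Synopsis, Methodology | Interruption, discontinuation or concomitant medication |
| Section 11.5.2, tolerability sentence | Therapy or discontinuation; interruption not listed |
| Section 11.5.1 | New or worsened unfavorable sign; no action needed |
| Section 11.5.2, general duty | All AEs, including those site staff observe |

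Take telangiectasia first seen at Week 8 that needs no action. Under the last two rows it is an AE. A site that reads the triggers as the threshold would record it only on the skin-reaction form. If every such sign were automatically an AE, the triggers would add nothing for these four signs, so that reading is reasonable. No sentence says which reading applies.

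**The case against.** A reader might infer that these signs become AEs only when they need therapy or a change in study drug, that the trial therefore yields no per-subject incidence, and that nobody need follow a sign past Week 12. The documents do not support any of the three.

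- The trigger sentences set conditions under which a reaction must be reported. Neither says that these are the only ones. The broad definition in Section 11.5.1, the duty in Section 11.5.2 to record what staff observe, and the label in Section 11.3.1 all point toward recording.
- A sign recorded as an AE enters the TEAE table by number of subjects and preferred term (Section 12.2.1). The signs are also scored per subject from Baseline to Week 12, so new onset can be derived. It is merely not prespecified.
- Recorded AEs are followed to resolution or stability with no end at Week 12, and Section 15.1 asks that side effects as well as AEs be documented to their conclusion. A gap remains only for a sign still present at Week 12 that was never recorded as an AE. Even there Section 15.1, a source-record rule, gives partial cover.

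Three further points are fair. The fourfold and fivefold figures need signs to vanish, or subjects to be absent, by the next visit, and nothing in the documents suggests how common that is. Early leavers are asked to complete the Week 8 assessments, which limits losses. And the only comparator is vehicle, so no table from this trial could show less atrophy than the marketed 0.05% products.

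What stands is that the planned summary does not count affected subjects once or isolate new findings, and that AE counts may depend on how a site reads the rule.

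**Conclusion.** The point holds as a cheap improvement. For the four present/absent signs, Section 12.2.2 and the synopsis prespecify neither an any-time nor a new-onset proportion. The understatement of the share ever affected ranges from none to several-fold (four- or fivefold in the extreme examples, on assumed counts), and Baseline findings can push the by-visit figure the other way. The by-visit table cannot show which applies.

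The AE texts do not settle whether a sign needing no action is recorded, and they differ on interruption, so TEAE counts and follow-up of such signs may vary by site. This is an ambiguity, not a rule that excludes these signs.

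Two limits apply. Section 12 announces a separate SAP that is not in the text available here and may already include the table. Such a table would not by itself settle the sites' AE rule. The primary efficacy analysis is not affected.

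**What to change.** **Analysis.** In Section 12.2.2 and the synopsis, add for each arm and each of the four signs the number and percent of subjects with the sign absent at Day 0 and present at any later visit, including early termination. Use as denominator the safety-set subjects without the sign at Day 0. Split the count into first seen on treatment and first seen at Week 12, and show whether the sign was present at the last observation. State how an early-termination visit is assigned, since Table 1 allows it up to 2 weeks after discontinuation. Keep the by-visit table.

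**Reporting.** Reconcile Sections 11.3.1, 11.5.1, 11.5.2 and the synopsis so that all sites apply one AE-recording rule to these signs. The rule should say what happens when a sign needs no action and whether interruption is a trigger.

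**Cost.** One extra table from data already collected at every visit, and short wording changes. Depending on the rule adopted, AE counts may rise slightly, and a few subjects with an unresolved sign at Week 12 may need follow-up under the existing AE provision.

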**Table 1. Study Design and Schedule of Assessments**

PROCEDURES	-Day -35 to -1 Screening	Day 0 Baseline	Week 2 (14 ± 3 days)	Week 4 (28 ± 3 days)	Week 6 (42 ± 3 days)	Week 8/ET a (56 ± 5 days)	Week 12/FU (Day 84 ± 7 days)
Informed consent	X						
Demographics	X						
Medical history b	X	X					
Previous psoriasis therapies b	X	X					
Inclusion/Exclusion criteria b	X	X					
Abbreviated physical examination c		X				X	X
Pregnancy testing d	X	X		X		X	X
Clinical laboratory tests e	X			X		X	
DLQI questionnaire		X		X		X	X
Investigator's Global Assessment	X	X	X	X	X	X	X
Psoriasis Signs Assessment (Target Lesion)	X	X	X	X	X	X	X
Photography (Target Lesion + 1 other selected Lesion)		X	X	X	X	X	X
Body surface area (BSA) affected evaluation	X	X	X	X	X	X	X
Local skin reactions evaluation		X	X	X	X	X	X
Randomization		X					
Review study drug application instructions		X	X	X	X		
Study drug weighed and dispensed		X	X	X	X		
Study drug collected and weighed			X	X	X	X	
Study diary calendar dispensed		X	X	X	X		
Review compliance with dosing / Diary			X	X	X	X	
Review adverse events		X	X	X	X	X	X
Review concomitant therapies	X	X	X	X	X	X	X
Study exit/end of study form							X

ET = early termination; FU = follow-up

a For subjects who discontinue early during the treatment period, all procedures outlined for the ET visit should be completed at the time of discontinuation or within 2 weeks of discontinuation.

b Update at Day 0 (Baseline).

c Height will be measured at Baseline only; vital signs, weight measurements and examinations of other abbreviated physical parameters will be performed at Baseline, Week 8, and Week 12.

d All female subjects of childbearing potential will undergo serum pregnancy testing at Screening, Week 4, and Week 8. In addition, urine pregnancy testing will be performed at Screening, Baseline (prior to randomization), and Week 12 (4-week post-treatment follow-up visit).

e Blood samples for laboratory tests will be collected at Screening prior to study drug application. Clinically significant laboratory findings at Week 4 or Week 8 will be repeated at the discretion of the investigator, and the subject will be followed until resolution (return to normal or to the baseline state) or until clinically stable as determined by the investigator.

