13. The investigator/evaluator will assess the signs of psoriasis (erythema, plaque elevation, and scaling) of the selected target lesion.
14. The investigator/evaluator will evaluate local skin reactions (itching, dryness, burning/stinging, skin atrophy, striae, telangiectasia and folliculitis) by observation and questioning the subjects as necessary.
15. Randomize the subject using the IRT system and record the assigned kit number in the source document and in the eCRF.
16. The study coordinator or designee will weigh each tube within the assigned kit and dispense them to the subject. A study diary calendar will also be dispensed.
17. The study coordinator or designee will instruct the subject on the proper application procedure for the study drug. For the first application, the subject will apply the study drug at the investigational center during the day under the direction of the study coordinator or designee. The study drug should be applied after all clinical assessments. The subjects will be asked to avoid exposure to direct sunlight and artificial ultraviolet light sources on the initial application day and thereafter. The study coordinator or designee will instruct the subjects to apply the study drug once daily at home.
18. Record any AEs reported spontaneously by the subject.
19. Schedule the next study visit at Week 2 (Day 14 ± 3 days).

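### The any-time grade 3 skin reaction table ignores the Baseline grade and includes Week 12, so it mixes persisting or returning psoriasis symptoms with new reactions

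*Combined protocol and SAP*

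**What the plan says.** Section 12.2.2 plans two summaries of local skin reactions.

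- The frequencies of all seven reactions "will be summarized by treatment group and visit".
- The percent of subjects, by arm, with itching, dryness or burning/stinging "graded at a level of 3, at any point in the study following the first application of study drug". The Safety part of the synopsis repeats this.

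The second summary does not mention the subject's grade before treatment. That grade exists: the row "Local skin reactions evaluation" in Table 1 is marked at Baseline and at Weeks 2, 4, 6, 8 and 12. Section 11.1.2 places the Day 0 assessment before randomization and adds: "The study drug should be applied after all clinical assessments". Week 12 falls four weeks after treatment ends.

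Table 4 grades by intensity alone. Grade 3 itching is "Intense itching that may interrupt daily activities and/or sleep" and grade 3 dryness is "Marked roughness". Neither scale asks about cause.

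**The concern.** Subjects enter with an IGA of 3 or 4 and a target lesion scoring at least 2 on scaling (Section 8.1), so itch and roughness may well be present before the first dose. Someone at grade 3 on Day 0 who is still at grade 3 at Week 2 enters the table as a subject with a severe local reaction.

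Randomization balances Day 0 grades but not how long they last. Section 5 describes the marketed 0.05% products of the same active ingredient as indicated for inflammation and itch. If IDP-122 works, carried-over grade 3 should clear sooner in its own arm. The vehicle arm then collects more carried-over counts, which offset any excess of new reactions on drug.

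The plan uses Baseline elsewhere. Section 12.2.3 has change from Baseline for laboratory values and vital signs, with shift tables for laboratory values, and Section 12.2.1 defines treatment-emergent events by onset. Section 12.2.1 also sets the primary safety analysis at Week 8 and tabulates later adverse events apart, whereas the grade 3 table runs on through Week 12.

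At stake is the reading of severe tolerability events for a product whose rationale in Section 5 includes fewer steroid adverse reactions.

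**Working it through.** The documents give no rate for local skin reactions, so there is no planned figure to reproduce. The stated power concerns IGA success and plays no part here. Every rate below is an assumption; only the arm sizes of 140 and 70 come from the plan.

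**Notation**

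- b: share at grade 3 on Day 0, taken as equal in both arms.
- p: share of those who are at grade 3 at one or more later visits.
- n: share of the rest who newly reach grade 3.

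**Formulas**

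- Table as planned = b × p + (1 − b) × n.
- New grade 3 as a share of all subjects = (1 − b) × n.
- Drug minus vehicle, as planned = (1 − b) × (difference in n) + b × (difference in p).

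**Main illustration:** n = 6% (drug) v 2% (vehicle), p = 40% v 80%, b = 25%.

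- Drug: 0.25 × 0.40 + 0.75 × 0.06 = 14.5%.
- Vehicle: 0.25 × 0.80 + 0.75 × 0.02 = 21.5%.
- New grade 3 only: 0.75 × 0.06 = 4.5% v 0.75 × 0.02 = 1.5%.
- In 140 drug subjects, 140 × 0.25 × 0.40 = 14 are carried over and 140 × 0.75 × 0.06 = 6.3 are new. In 70 vehicle subjects, 14 are carried over and 1.05 are new.
- Carried-over disease is 14/20.3 = 69% of the drug count and 14/15.05 = 93% of the vehicle count.

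**Varying the persistence gap**, with n held at 6% v 2%:

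| Persistence, drug v vehicle | Drug minus vehicle | Table at b = 25% | Sign reverses above |
|---|---|---|---|
| 40% v 80% | 0.04 − 0.44b | 14.5% v 21.5% | 0.04/0.44 = 9.1% |
| 60% v 80% | 0.04 − 0.24b | 19.5% v 21.5% | 0.04/0.24 = 16.7% |
| 70% v 80% | 0.04 − 0.14b | 22.0% v 21.5% | 0.04/0.14 = 28.6% |
| 50% v 50% | 0.04 − 0.04b | 17.0% v 14.0% | never |

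In the last row a 3:1 ratio of new reactions (4.5% v 1.5%) appears as about 1.2:1. At b = 0 every row gives 6% v 2%, which is the undistorted comparison.

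**Other inputs.** With n = 5% v 1% and p = 40% v 70%, the difference is 0.04 − 0.34b. The table shows 8.5% v 7.9% at b = 10% and 12.0% v 14.8% at b = 20%, and the sign reverses above 11.8%. Combining p = 40% v 70% or 25% v 75% with n = 5% v 1% or 8% v 2% gives reversal points from 7% to 17%.

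Disease returning at Week 12 is not modelled separately. It would add counts after treatment has stopped, and the documents do not show in which arm.

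**The case against.** The case against has real weight.

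- **Grades are shown elsewhere.** Section 12 says categorical parameters are given as number and percent in each category. The by-visit summary should therefore show grades 0 to 3 by arm at every visit, Baseline and Week 12 included. A reader might infer that the grade 3 table is the only severity summary, or that Baseline grades go unused; the documents support neither. What stands is that this display is cross-sectional: clearing in some subjects cancels new reactions in others.
- **Reactions needing action become adverse events.** Section 11.3.1 requires a report when a reaction needs therapy or causes interruption or discontinuation, and adverse events are summarized by severity. But a new grade 3 score tolerated without those steps may never become one.
- **The Day 0 reading is not counted.** A reader might say the table measures untreated psoriasis. It does not: it mixes persisting symptoms with new ones, in unknown proportion.
- **Reversal is not established.** It needs both common Baseline grade 3 and unequal persistence. One later grade 3 reading, such as at Week 2, counts as persistence, so a 40-point gap is demanding. The only effect size in the plan, 33.3% v 9.7% (23.6 points), is for a different endpoint at Week 8.
- **A separate SAP is promised.** Section 12 leaves the full analysis description to a document that is not in the text reviewed, and a shift table may be specified there. The protocol wording would still need to match it.

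Atrophy, striae, telangiectasia and folliculitis are not in the grade 3 table, so the defect does not reach them.

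**Conclusion.** The point holds as a limited one. As worded, the table counts grade 3 symptoms that were present before the first dose and persist, and symptoms that return off treatment. No within-subject comparison with Baseline is planned for local skin reactions.

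Under the assumptions shown, a drug-caused excess is diluted whenever some subjects start at grade 3 that persists. It reverses only if Baseline grade 3 exceeds about 9% (persistence 40% v 80%) or about 17% (60% v 80%). With equal persistence it never reverses, and with Baseline grade 3 near zero nothing is distorted. Because the documents give none of these rates, reversal is a possibility and not a forecast.

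The risk attaches to this one table, not to the whole safety assessment. The summary is descriptive, so no test, alpha level, sample size or efficacy conclusion is affected. It is worth correcting because the correction is nearly free.

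**What to change.** In Section 12.2.2 and the Safety part of the synopsis, add by treatment group, for itching, dryness and burning/stinging:

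1. A shift table from the Baseline grade to the worst on-treatment grade, through Week 8.
2. The percent with new grade 3 among subjects below grade 3 at Baseline, with subjects already at grade 3 shown as their own row.
3. Week 12 grades, shown separately.

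Keep the any-time grade 3 table as a secondary display. If a separate SAP already has such a table, align the protocol text with it.

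The cost is a few sentences and one extra descriptive table; no new data are needed. There is one drawback: the new-grade-3 rate leaves out subjects who start at grade 3, so it must not appear without the shift table. Even there, the cell for grade 3 at both times cannot separate persistence from clearing followed by a new reaction.
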